6.4 Efficacy Variables

6.4.1 Qualitative assessment for Flortaucipir and Diagnostic Performance

The flortaucipir scan image will be visually interpreted. The scans will be classified as either

- Not consistent with an AD pattern (τ AD-)
- AD pattern (τ AD+)
- AD pattern and likely to progress (τ AD++)

6.4.2 Quantitative assessment of images for Flortaucipir (SUVr based)

For the flortaucipir image, standard uptake value ratios (SUVr) will be calculated to estimate tau globally. SUVr will be calculated after the visual read and only on scans that

were $\tau\text{AD}+$ or $\tau\text{AD}++$. For global assessment, a target region derived statistically with a Multiblock Barycentric Discriminant Analysis (MUBADA) method will be used.

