8.1.1. Population for Analysis

The safety analysis population will include all eligible patients who enroll in ¹⁸F-AV-1451-A24 (A24) and have received at least one dose of flortaucipir F 18 injection. Efficacy analysis population will include all subjects in safety population, and with a valid flortaucipir F 18 scan assessment (quantitative and/or qualitative).

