8.2. Analysis

Descriptive analyses will be applied to summarize patients' demographic and baseline characteristics, and qualitative and quantitative assessments of the flortaucipir F 18 PET image.

Adverse events including injection site reactions will be summarized in terms of number and percentage of subjects experiencing an AE. The summary will be further broken down by system organ class (SOC) and preferred term using Medical Dictionary for Regulatory Activities (MedDRA) terms. Adverse events will also be presented by severity, relationship to treatment and seriousness. All subjects who experience SAEs or who discontinue due to AEs will be summarized.

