5.2 Changes from the Analyses Planned in the Protocol/CIP

There were no changes in the analyses planned in the Protocol/CIP at the time of preparing this statistical analysis plan.

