8.1.3 Efficacy Population

The efficacy analysis population will include all subjects in the safety population that have a valid flortaucipir scan assessment [SUV_r (quantitative) and/or visual reads (qualitative)].

Any scans deemed to be unquantifiable due to technical reasons will be excluded from SUV_r related analyses.

All analyses involving imaging outcomes will be based on the efficacy population.

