8.9.1 Qualitative Assessment of Images

The visual read results will be categorized as τ AD+, τ AD++ and τ AD-. The visual read results will be summarized by frequency distribution (count and percentage) for the efficacy population by subject eligibility and overall.

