8.9.2 Quantitative Assessment of Images

The Screening MUBADA SUV_r will be summarized using descriptive statistics [n, mean, SD, median, minimum and maximum values, and quartiles (25th and 75th percentile)] by visual read results (τ AD+, τ AD++), subject eligibility, and overall.

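### Does limiting SUVr to scans read as τAD+ or τAD++ distort the quantitative summary or depart from the protocol?

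*SAP*

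**What the plan says.** SAP 6.4.1 sorts every scan by visual read into τAD−, τAD+ or τAD++. SAP 6.4.2 then restricts quantification: "SUVr will be calculated after the visual read and only on scans that" fell in one of the two positive categories. No reason is given.

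SAP 8.9.1 counts all three read categories in the efficacy population, by subject eligibility and overall. SAP 8.9.2 summarises MUBADA SUVr "by visual read results (τ AD+, τ AD++), subject eligibility, and overall", with n among the statistics.

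On populations, SAP 8.1.3 says "All analyses involving imaging outcomes will be based on the efficacy population". Membership needs a valid SUVr "quantitative) and/or visual reads (qualitative" assessment. The only SUVr exclusion named in that section is for technically unquantifiable scans. Protocol 8.1.1 sets the same condition: "with a valid flortaucipir F 18 scan assessment (quantitative and/or qualitative".

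Protocol 8.2 plans descriptive summaries of "qualitative and quantitative assessments of the flortaucipir F 18 PET image" and sets no limit by read result. SAP 5.2 states: "There were no changes in the analyses planned in the Protocol/CIP" when the SAP was prepared.

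**The concern.** Three things look wrong.

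- **Selection on the read.** Adjacent tables use the same labels, eligibility and overall, for different sets of scans. A reader could take the overall SUVr in 8.9.2 as the average tau signal of the efficacy population, when it is the average among positive reads.
- **An undeclared narrowing.** The limit appears in SAP 6.4.2, not in Protocol 8.2, and SAP 5.2 reports no change from the protocol's analyses. SAP 8.1.3 mentions the technical exclusion but not the one based on the read.
- **A missing group.** τAD− scans get a count but no SUVr. SUVr can be compared between τAD+ and τAD++, but not across the boundary between a negative and a positive read.

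If these points held, the quantitative results would be open to misreading and the SAP would have departed from the protocol without saying so.

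**Working it through.** **1. Are the passages compatible?**

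| Place | What it requires | Compatible with SAP 6.4.2? |
|---|---|---|
| SAP 8.9.2 | SUVr by τAD+ and τAD++, by eligibility, overall, with n | Yes: it names exactly the two categories that have an SUVr |
| SAP 8.9.1 | Counts of all three reads | Yes: every scan is read, so all three can be counted |
| SAP 8.1.3 | Imaging analyses use the efficacy population, entered by SUVr and/or read | Yes: a member may have no SUVr |
| Protocol 8.1.1 | Valid assessment, quantitative and/or qualitative | Yes: same allowance |
| Protocol 8.2 | Describe qualitative and quantitative assessments | Yes: it names neither SUVr nor MUBADA and does not say every scan is quantified |
| SAP 5.2 | No change from the protocol's analyses | Not shown to be wrong: the SAP supplies a detail the protocol leaves open |

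Under 6.4.2 an SUVr exists only after a positive read, so anyone with an SUVr also has a read. The efficacy population is in practice the subjects with a valid read, τAD− included.

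**2. Can the reader recover what is left out?** Let R be the number of valid reads, N− the number of τAD− reads, and k the positive scans that cannot be quantified. Then

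overall n in 8.9.2 = R − N− − k.

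SAP 8.9.1 reports R and N−, and 8.9.2 reports its own n, so k follows by subtraction. The τAD+ and τAD++ rows in 8.9.2 also add up to the overall n, which shows that no third category is in it.

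**3. How many scans are affected?** The documents give no τAD− share, so p below is an assumption. SAP 4.5 plans about 500 enrolled. Taking R = 500 (all enrolled are scanned with valid reads) and k = 0:

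scans without SUVr = 500 × p; scans with SUVr = 500 × (1 − p).

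| Assumed p | Without SUVr | With SUVr |
|---|---|---|
| 0.10 | 50 | 450 |
| 0.20 | 100 | 400 |
| 0.30 | 150 | 350 |
| 0.40 | 200 | 300 |
| 0.50 | 250 | 250 |

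These figures show scale only. How far the overall mean would move cannot be estimated, because the documents give no SUVr values.

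**4. Does anything planned depend on the missing values?** The objectives in Protocol 2 and SAP 3 are to pre-screen patients and to enlarge the safety database. SAP 7.1 summarises one group descriptively, SAP 7.4 plans no interim analysis and SAP 7.8 no subgroup analysis. SAP 4.5 gives no alpha, power or effect size. No comparison between τAD− and τAD+ is planned.

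**The case for a change.** The strongest case for a change starts from the introduction to both documents. They describe a hypothesis about both ends of the tau range (no tau, and a large burden) and call testing it the overarching goal. Scans read as not AD-pattern are the ones left without a number, and the regional assessment in SAP 6.4.3 is itself a visual read, shown only in a listing. Copies of all scans go to the sponsor (Protocol 7.6), so quantifying the rest would need no new visit or scan. Labelling the rows would cost only words.

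Part of this stands. The shared row labels are loose, and subject eligibility is not defined for either table. It could mean this study's entry criteria or suitability for a later therapeutic trial. If it required a positive read, the eligible row in 8.9.2 would lose no scans to the restriction; otherwise it could. That gap would remain if every scan were quantified, so it adds nothing to the SUVr argument.

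The rest does not carry. The hypothesis is about speed of progression and response to therapy. Participation here ends with one scan and a follow-up call, so SUVr on τAD− scans could not test it. Comparing SUVr across the negative-positive boundary is a reasonable research question, but it is not one the plan asks. That the sponsor holds the scans does not show what extra processing would involve, since procedures are left to an imaging manual outside these documents. A sequence of reading first and quantifying only AD-pattern scans fits a programme looking for patients in a certain tau range. That motive is an inference, since the documents do not state it.

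**Conclusion.** No change follows. The facts are as described: every SUVr row in SAP 8.9.2 contains visually positive scans only. But the rule is explicit and prespecified, the summary section is built around it, and no passage in either document is breached. Followed as written, the plan gives a sound description of SUVr among positive reads and a full count of all reads.

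On the assumed τAD− share of 10% to 50% and about 500 valid reads, 50 to 250 scans have no SUVr. No error rate, power calculation or decision is affected. Quantifying those scans would be an optional extension that reverses a deliberate choice to answer an added question. The remaining gaps are a row label saying that the 8.9.2 summaries are among τAD+ and τAD++ scans, and a definition of eligibility. Analysts can settle both in table titles and footnotes.

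This conclusion rests on the study staying descriptive. It would need another look if a comparison involving τAD− SUVr were added.

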6.4.3 Increased neocortical Flortaucipir activity

The hemisphere and region of increased neocortical flortaucipir activity will be identified by visual read.

The hemisphere will be classified as either left or right and the region is classified as

- Anterior Lateral Temporal
- Posterior Lateral Temporal
- Occipital
- Parietal
- Precuneus
- Frontal

6.5 Drug Concentration Measurements and Pharmacokinetic Parameters

No pharmacokinetic parameters or drug concentration measurements will be collected during this study.

6.6 Safety Assessments

6.6.1 Extent of Exposure and Compliance to Study Treatment

During the flortaucipir imaging session, subjects will receive a single IV bolus administration target dose of 370 MBq (10 mCi) of flortaucipir F 18 injection followed by a saline flush. At approximately 75 minutes following injection, a continuous 30-minute brain scan will begin. Exposure to study drug will be summarized using the total administered dose at the scan visit for flortaucipir F 18 injection.

6.6.2 Adverse Events

The investigator's verbatim term of adverse events will be mapped to system organ class (SOC) and preferred terms using the current version of the Medical Dictionary for Regulatory Activities (MedDRA).

Treatment-emergent AEs (TEAEs) are undesirable experiences, signs, or symptoms that begin or worsen in intensity or frequency at the time of or after the administration of study drug at the imaging visit, and prior to the end of observation windows defined as

following: the TEAE window will be from injection of flortaucipir F 18 until 48 hours post flortaucipir F 18 injection. These will be recorded on the AE page of the electronic case report form (eCRF).

Serious AEs (SAEs) are events that result in one of the following outcomes or constitute one of the following events:

- Death
- Initial or prolonged hospitalization (other than that required by protocol; “social hospitalization” or any hospitalization for non-medical reasons does not constitute an SAE)
- A life-threatening experience (that is, immediate risk of dying)
- Persistent or significant disability/incapacity
- Congenital anomaly/birth defect
- Considered significant by the investigator for any other reason

Important medical events that may not result in death, are life-threatening, or require hospitalization may be considered serious adverse drug events when, based upon appropriate medical judgment, they may jeopardize the patient and may require medical or surgical intervention to prevent one of the outcomes listed in this definition.

For the summarization of TEAEs by seriousness, events recorded with missing seriousness will be summarized as serious.

Investigators will be instructed to report their assessment of the potential relatedness of each AE to protocol procedure or study drug. The assessment of the relationship of an AE to the administration of the investigational product is a clinical decision based on all available information at the time of the completion of the eCRF. For the summarization of TEAEs by relationship to study drug or protocol procedure, events recorded with missing relationship will be summarized as Related.

In addition to assessing the relationship of the administration of the investigational product to AEs, an assessment is required of the severity of the event. The following classifications should be used:

Mild:

A mild AE is an AE, usually transient in nature and generally not interfering with normal activities.

Moderate:

A moderate AE is an AE that is sufficiently discomforting to interfere with normal activities.

Severe:

A severe AE is an AE that incapacitates the subject and prevents normal activities. Note that a severe event is not necessarily a serious event. Nor must a serious event necessarily be severe.

For the summarization of TEAEs by intensity, events recorded with missing intensity will be summarized as Severe.

6.6.3 Other Observations Related to Safety

6.6.3.1 Vital Signs

Vital signs (pulse rate, respiratory rate, and supine blood pressure) will be taken at the screening visit. Weight will be measured, lightly clothed during the imaging visit.

6.6.3.2 Electrocardiogram (ECG)

A resting 12-lead electrocardiogram will be recorded as part of the screening visit, unless an ECG was performed within twelve months of the flortaucipir PET Imaging Visit and is available for review.

6.7 Pharmacodynamics Parameters

No pharmacodynamics parameters will be collected during this study.

7 STATISTICAL METHODS

7.1 General Methodology

All values will be summarized as a single group, early symptomatic AD. Frequency distributions including counts and percentages will be reported for all categorical outcomes. Summary statistics including number of subjects [N], mean, standard deviation [SD], median, quartiles, minimum and maximum values will be presented for all continuous outcomes.

All statistical analyses will be performed using SAS® version 9.3 or higher. Patient listings of all data from the eCRF as well as any derived variables will be presented.

7.2 Adjustments for Covariates

Not applicable for the primary analyses.

7.3 Handling of Dropouts or Missing Data

Dropout subjects will not be replaced in this study. For situations with no rules for handling missing data, the default will be no imputation.

7.4 Interim Analyses and Data Monitoring

No interim analysis or data monitoring is planned for this study

7.5 Multi-center Studies and Pooling of Centers

This study will be conducted in approximately 15 centers. The data from all centers will be pooled. The pooled data will be analyzed and presented.

7.6 Multiple Comparisons/Multiplicity

No adjustment for multiplicity will be performed in this study.

7.7 Active-Control Studies Intended to Show Equivalence

Not applicable to this study.

7.8 Examination of Subgroups

No subgroup analysis will be performed.

8 STATISTICAL ANALYSIS

8.1 Analysis Populations

8.1.1 Enrolled Population

The enrolled population will consist of all subjects who signed informed consent and have data captured in the clinical database. Disposition information will be summarized using the enrolled population.

8.1.2 Safety Population

The safety analysis population will include all subjects who enroll in ¹⁸F-AV-1451-A24 (A24) and have received at least one dose of flortaucipir F 18 injection.

All demographic, baseline and safety endpoints will use the safety population.

8.1.3 Efficacy Population

The efficacy analysis population will include all subjects in the safety population that have a valid flortaucipir scan assessment [SUV_r (quantitative) and/or visual reads (qualitative)].

Any scans deemed to be unquantifiable due to technical reasons will be excluded from SUV_r related analyses.

All analyses involving imaging outcomes will be based on the efficacy population.

8.2 Disposition of Subjects

The enrolled population will be represented in the disposition table. The disposition table will include a summary of the analysis populations, number of completed and discontinued subjects, and the reasons for discontinuation. All percentages will be based on the safety population.

Disposition data will be presented in a listing.

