4 STUDY DESIGN

4.1 General Design

Study ¹⁸F-AV-1451-A24 is a multicenter screening study in subjects with early symptomatic AD (defined as prodromal AD and mild dementia due to AD).

All subjects will provide informed consent before starting any study procedures. This prescreening study targets subjects who are interested in participating in AD therapeutic clinical trials and have expressed a preliminary interest in a trial like the LMDC trial, and who are not known to have met any of the exclusion criteria for trials like LMDC based on medical history and clinical examination. However, consent for this protocol does not constitute consent for the LMDC trial or any other trials, and subjects who qualify for this protocol may still fail to qualify for trials like LMDC or other trials based on the results of this protocol or based on additional testing performed in those subsequent trials.

Screening assessments may take place over several days and will be performed within 30 days prior to flortaucipir F 18 injection. Screening assessments will include demographic information, cognitive testing, disease history, concomitant medications, vital signs, ECG and medical history. Subjects who are deemed eligible to continue will complete a flortaucipir PET scan.

A physician or a licensed/credentialed medial professional (i.e., a PET technologist, imaging center nurse or a regional equivalent) designated by the site principal investigator must assess or evaluate the subject prior to administration of flortaucipir F 18 injection to determine if they are still suitable to undergo the scan.

All subjects will receive a single IV bolus administration target dose of 370 MBq (10 mCi) of flortaucipir F 18 injection followed by saline flush. At approximately 75 minutes following injection, a continuous 30-minute brain scan will be performed.

The injection site will be observed for excessive inflammation or damage to the surrounding tissue at the injection site. Adverse events will be continuously monitored during the flortaucipir PET imaging visit. Subjects who experience an adverse event will not be discharged from the imaging center until the event has resolved or stabilized. A follow-up phone call to the subject, or informant where applicable, will be conducted within 2 or 3 business days of the imaging day, but not before 48 hours post-injection, to confirm subject well-being and to collect any new adverse events.

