A physician or a licensed/credentialed medial professional (i.e., a PET technologist, imaging center nurse or a regional equivalent) designated by the site principal investigator must assess or evaluate the subject prior to discharge from the imaging center to evaluate the subject's readiness for discharge.

Subjects who meet eligibility criteria will participate in this protocol until they complete their flortaucipir PET scan, or they discontinue, withdraw consent, or if the sponsor decides to end this protocol early.

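### SAP 8.2 tabulates disposition for enrolled subjects but takes every percentage over dosed subjects, so discontinuation before injection is overstated whenever an enrolled subject goes undosed

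*SAP*

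**What the plan says.** Two sections of the SAP assign the disposition table to the enrolled population. Section 8.1.1 states "Disposition information will be summarized using the enrolled population", and section 8.2 states "The enrolled population will be represented in the disposition table". Section 8.1.1 defines the group: "The enrolled population will consist of all subjects who signed informed consent and have data captured in the clinical database". Neither eligibility nor dosing is part of that definition.

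Section 8.2 lists the contents of the table: the analysis populations, the numbers completing and discontinuing, and the reasons for discontinuing. It then sets the denominator for the whole table: "All percentages will be based on the safety population".

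Section 8.1.2 limits the safety population to enrolled subjects who "have received at least one dose of flortaucipir F 18 injection". It is therefore a subset of the enrolled population, and a strict subset as soon as one enrolled subject is not injected.

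**The concern.** Numerators come from the larger group and the denominator from the smaller one. An enrolled subject who leaves before injection adds one to the discontinued row and to a reason row, but nothing to the base.

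The plan foresees such subjects. Consent comes before every study procedure. SAP 4.1 says of the screening period: "Screening assessments may take place over several days and will be performed within 30 days prior to flortaucipir F 18 injection". It also requires the subject to be assessed again before injection "to determine if they are still suitable to undergo the scan". Subjects who already meet the eligibility criteria stay in the study until the scan is done, "or they discontinue, withdraw consent, or if the sponsor decides to end this protocol early". Any of these exits can come before the dose.

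What is at stake is how attrition between consent and scan is reported. In a study whose primary objective is pre-screening, that attrition is informative. As written, the table can overstate it and can show completed and discontinued percentages that add to more than 100%.

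**Working it through.** **Inputs**

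- Planned enrolment: E = 500, approximate (SAP 4.5).
- Undosed share of enrolled subjects: u. The documents give no figure, so it is assumed over 0% to 50%.
- Dosed subjects, the safety population: S = E(1−u).
- Assumed: each undosed enrolled subject is coded as discontinued, and every enrolled subject is classed as either completed or discontinued.

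The plan states no disposition percentage, so there is no figure of its own to reproduce.

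**Formulas**

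- Pre-dose discontinuation as printed under 8.2: uE/S = u/(1−u).
- The same count over enrolled subjects: uE/E = u.
- Overstatement factor: E/S = 1/(1−u).
- Completed plus discontinued as printed: E/S = 1/(1−u).

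**Results for E = 500**

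| Undosed (assumed) | Undosed / dosed | Printed under 8.2 | Over enrolled | Completed + discontinued |
|---|---|---|---|---|
| 0% | 0 / 500 | 0% | 0% | 100% |
| 1% | 5 / 495 | 1.0% | 1.0% | 101.0% |
| 5% | 25 / 475 | 5.3% | 5.0% | 105.3% |
| 10% | 50 / 450 | 11.1% | 10.0% | 111.1% |
| 20% | 100 / 400 | 25.0% | 20.0% | 125.0% |
| 30% | 150 / 350 | 42.9% | 30.0% | 142.9% |
| 50% | 250 / 250 | 100% | 50.0% | 200% |

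The percentages depend only on u, not on 500. Since u/(1−u) exceeds u for every u above zero, the direction does not rest on the assumed values. A pre-dose figure passes 100% only when more than half of the enrolled subjects are undosed. If the table prints a percentage beside the enrolled count itself, that percentage is the one in the last column.

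**With some discontinuations after dosing.** SAP 8.2 names a single discontinued row, which would mix pre-dose and post-dose exits. Take 20% undosed and, as a further assumption, 5 post-dose discontinuations. The row holds 105 subjects: 105/400 = 26.25% as printed, against 105/500 = 21.0% of enrolled. The factor is again 1.25. The completed row is 395/400 = 98.8% as printed, against 395/500 = 79.0% of enrolled. The printed pair adds to 500/400 = 125.0%.

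**The case against.** The strongest reply is that the effect may be negligible. Protocol 5.3.1 and 5.3.2 use enrolment to mean meeting the entry criteria, and Protocol 10.6 calls for case report forms for enrolled patients. Screen failures may therefore never reach the database. Undosed subjects would then be only those lost between eligibility and injection, over a period of about 30 days. At 1% to 5% undosed the printed figure moves by 0.3 percentage points at most. This stands as a caution about size: the upper rows of the table are illustrations, not forecasts. It does not remove the mismatch, because the SAP's own definition of enrolled does not require eligibility, and one eligible subject who withdraws before the dose is enough to trigger it.

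A second reply is that an undosed subject has to be coded as discontinued before any row is inflated, and that SAP 4.1 speaks of discontinuing only for subjects who meet the eligibility criteria. This is correct, and the coding of screen failures is not stated. An eligible subject who withdraws before injection is still a discontinuation on that reading.

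A third reply is that a dosed denominator has a proper use. In the example above, 98.8% is the correct completion rate among subjects who received the tracer. This also stands, and the fix keeps room for it. That rate, however, needs dosed subjects in the numerators too, and 8.2 does not restrict them.

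Finally, the study is descriptive and single-arm, and the table prints counts alongside a listing, so a reader can recompute the shares. This limits the consequence but does not make the percentages right.

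**Conclusion.** The concern holds. SAP 8.2 sets a denominator that excludes some of the subjects its numerators can include, and no other section supplies a different one. If any enrolled subject is undosed and coded as discontinued, discontinuation before injection is overstated by the factor 1/(1−u).

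The size cannot be fixed from the documents: nothing at 0% undosed, below rounding at 1%, 0.3 points at 5%, 5 points at 20%. Totals above 100% further require that every enrolled subject be classed as completed or discontinued.

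This is a reporting error in one descriptive table. Demographic, safety and imaging summaries use their own populations and are not touched. It should be corrected before the table is programmed, but it does not threaten either study objective.

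**What to change.** Replace the denominator sentence in SAP 8.2 with: *Percentages for analysis populations, completion, discontinuation and reasons for discontinuation will be based on the enrolled population.* This brings 8.2 into line with 8.1.1. Completed plus discontinued then totals 100% when every enrolled subject is classed as one or the other.

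If retention after dosing is also of interest, add a separate block limited to the safety population in both numerator and denominator.

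The cost of the main change is one sentence in the SAP and one denominator in the table program. No new data are needed.
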